9.5.2.3 Reporting of Pregnancies Occurring During the Study

Study center personnel must report every pregnancy from the time the patient signs the ICF until 30 days after the last dose of IP. Within 24 hours of learning of the pregnancy, the study center personnel must report the event to Global Drug Safety on the Clinical Trial Pregnancy Form and fax it to the SAE/pregnancy fax number provided in [Section 9.5.2.2](#), even if no AE has occurred. Pregnancies in female partners of male patients occurring during the timeframe described above must also be reported.

Any pregnancy of a patient treated with IP must be followed to term and the outcome reported by completing a follow-up Clinical Trial Pregnancy Form. If the pregnancy is associated with an SAE (eg, if the mother is hospitalized for hemorrhage), a separate SAE Form for Clinical Trials must be filed as described in [Section 9.5.2.2](#) with the appropriate serious criterion (eg, hospitalization) indicated in addition to the pregnancy form.

9.5.2.4 Potential Hy's Law Cases

The criteria for potential Hy's Law cases are as follows:

- ALT or AST $\geq 3 \times$ ULN and
- Total bilirubin $\geq 2 \times$ ULN and
- Alkaline phosphatase $< 2 \times$ ULN

Study center personnel must report every patient who meets these potential criteria. Typically, all 3 analytes will be obtained from the same sample, but they may come from multiple samples taken within a 24-hour period. This requirement applies from the time the ICF is signed for the study until 30 days after the final protocol-defined study visit or the last known dose of IP (if the final visit does not occur).

A laboratory alert for potential Hy's Law cases will be in place, and the laboratory must notify investigators and the Sponsor immediately when the above criteria have been met. A potential Hy's Law case must be faxed to the Sponsor on an AE of Interest Form as soon as possible (within 24 hours of learning of the potential Hy's Law) to the SAE/pregnancy fax number stated in [Section 9.5.2.2](#), even if no AE has occurred. The eCRF for potential Hy's Law cases must be completed within 7 calendar days. Every effort to determine the cause of the liver enzyme abnormalities must be made, and close monitoring should be initiated in conjunction with the Study Physician and in accordance with the [FDA Guidance for Industry: Drug Induced Liver Injury - Pre-Marketing Clinical Evaluation, July 2009](#).

9.5.2.5 Clinical Laboratory Determinations

Blood and urine samples for clinical laboratory tests will be collected as detailed in the Schedule of Evaluations ([Section 2.0](#)). During screening, the Investigator will assess the clinical significance of any values that are outside the reference ranges provided by the central laboratory; patients with abnormalities judged to be clinically significant will be excluded from the study.

Patients will be asked to fast overnight or for at least 8 hours before arriving at the study center for appointments involving the collection of clinical laboratory blood tests.

The following clinical laboratory levels will be measured:

Hematology: Absolute and differential white blood cell count, erythrocyte count, hemoglobin, hematocrit, platelet count, and red blood cell indices (mean corpuscular volume, mean corpuscular hemoglobin, and mean corpuscular hemoglobin concentration)

Chemistry: Sodium, potassium, calcium, chloride, bicarbonate, magnesium, gamma glutamyl transferase, phosphate, glucose, blood urea nitrogen, creatinine, creatine phosphokinase, total protein, alkaline phosphatase, albumin, bilirubin (total; direct; indirect), ALT, AST, total cholesterol, low-density lipoprotein, high-density lipoprotein, and triglycerides

HbA1c and fasting insulin: As specified in the Schedule of Evaluations ([Section 2.0](#))

Urinalysis: Specific gravity, pH, protein, glucose, ketones, and blood

Thyroid function: Thyroid function test at Screening (Visit 1) and periodically as specified in the Schedule of Evaluations ([Section 2.0](#))

UDS: Benzoylcegonine (cocaine), barbiturates, amphetamines, benzodiazepines, cannabinoids, opiates, methadone, phencyclidine, performed at Screening (Visit 1), and periodically as specified in the Schedule of Evaluations ([Section 2.0](#)) (and at Investigator's discretion)

Serum β -hCG: Serum β -hCG will be performed at Screening (Visit 1) and periodically as specified in the Schedule of Evaluations ([Section 2.0](#)) (and at Investigator's discretion)

Hepatitis screening: Hepatitis–C virus antibody, hepatitis–B surface antigen, and hepatitis-B core antibody total will be tested. Reflex hepatitis-B core antibody IgM will be performed for all hepatitis–B core antibody total positive or reactive results. Positive test results will be sent for confirmation testing. Hepatitis screening is to be conducted at Screening (Visit 1) on *de novo* patients only (new patients who did not participate in RAP-MD-04).

Clinical laboratory tests may be performed under special circumstances (and at Investigator’s discretion).

A negative UDS (except for benzodiazepines if prescribed by the Investigator as per the protocol) is required before Baseline (Visit 2) for the patient to continue in the study. A UDS may be performed at any time during the study at the discretion of the Investigator. A patient with a positive UDS for benzodiazepines or opiates at any visit may be allowed to continue in the study provided the patient has been prescribed the medication and it is being used for legitimate medical purpose in the Investigator’s judgment.

Serum pregnancy test will be performed as specified in the Schedule of Evaluations (Section 2.0). Positive results on the pregnancy test at Screening (Visit 1) will exclude patients from participating in the study. Positive pregnancy test results during the study will result in patient termination from the study.

Other laboratory assessments may be repeated at any visit if there was an abnormal finding at the most recent previous evaluation or if additional information is clinically necessary to appropriately evaluate the patient’s current condition, follow up, and/or manage an adverse experience.

A central laboratory will be used to evaluate all urine and blood samples, which will be collected, processed, and stored according to the instructions provided by the laboratory.

9.5.2.6 Vital Signs

Vital signs (pulse rate, systolic and diastolic BP, oral or tympanic temperature, and body weight) will be assessed at every visit during the OLTP. Height will be assessed at Visit 1 for *de novo* patients only (Section 2.0).

BP and radial pulse rate will be measured in the supine position followed by the standing position. The standing measurements should be assessed after a sufficient amount of time has been elapsed to allow the BP to equilibrate in the standing state.

Radial pulse rate should be measured after BP measurements. BP may be measured manually or by machine, but radial pulse rate should only be measured manually and for a sufficient time to acquire an accurate measurement.

Patients should be instructed not to wear clothing with tight sleeves when they come for clinic visits. Additionally, patients should be kept as calm and undisturbed as possible while BP and pulse rate measurements are taken (eg, there should be no talking while the BP is being measured). The same arm and BP cuff (appropriate to the arm circumference) should be used for all BP measurements.

Whenever possible, the patient's weight will be measured at the same time of day; patients should wear their usual indoor clothing, but take off their jacket and shoes. For each patient, body weight should be determined using the same equipment during the study after ensuring its proper calibration.

9.5.2.7 *Electrocardiograms*

A 12-lead ECG will be performed at the visits outlined in the Schedule of Evaluations ([Section 2.0](#)). The ECGs will be performed and electronically transmitted to a central ECG laboratory for analysis according to the instructions provided by the central ECG laboratory. Measurements (in msec) will be recorded for the following parameters: PR interval, QRS duration, and uncorrected QT interval. QTcB (Bazett corrected QT interval) and QTcF (Fridericia corrected QT interval) will be calculated.

The overall interpretation and determination of the clinical relevance of ECG findings using the central ECG interpretation laboratory report will be the responsibility of the Investigator and will be recorded in the patient's eCRF. For eligibility criteria, the values reported on the central ECG interpretation report will be used (not the values printed on the tracing itself).

[REDACTED]

9.5.2.8.3 *Brief Psychiatric Rating Scale - Positive Symptoms Subscale*

The BPRS is an 18-item evaluation that assesses psychiatric symptoms and unusual behavior ([Overall and Gorham, 1962](#)). The BPRS+ is a subset of the BPRS that assesses 4 components of the BPRS+ related to the degree of psychosis: Conceptual Disorganization, Suspiciousness, Hallucinatory Behavior, and Unusual Thought Content. Only the 4 items of the BPRS+ subscale will be collected and analyzed. The BPRS+ will be administered by the Investigator or designee with extensive professional training and experience in assessing mental illness.

9.5.2.8.4 *Clinician Administered Dissociative States Scale*

The Clinician Administered Dissociative States Scale (CADSS) is a 28-item clinician-administered measure of perceptual, behavioral, and attentional alterations occurring during active dissociative experiences composed of 23 subjective self-reported and 5 objective observer-reported ratings, each scored from 0 (not at all) to 4 (extremely). Only the 23 subjective items will be collected and analyzed. The CADSS provides a validated assessment of dissociative states sensitive to change over time and amenable to repeated measures (Bremner et al, 1998). The CADSS will be administered by the Investigator or designee with extensive professional training and experience in assessing mental illness.

[REDACTED]

[REDACTED]

[REDACTED]

[REDACTED]

[REDACTED]

9.5.6 Schedule of Assessments

The schedule of study procedures and assessments is tabulated by visit in the Schedule of Evaluations in [Section 2.0](#). The descriptions of the procedures to be performed at each visit are provided in the following sections.

[REDACTED]

[REDACTED]

| [REDACTED]

| [REDACTED]

| [REDACTED]

| [REDACTED]

| [REDACTED]

| [REDACTED]

| [REDACTED]

| [REDACTED]

| [REDACTED]

| [REDACTED]

| [REDACTED]

| [REDACTED]

| [REDACTED]

| [REDACTED]

| [REDACTED]

| [REDACTED]

| [REDACTED]

| [REDACTED]

| [REDACTED]

█ [REDACTED]

█ [REDACTED]

█ [REDACTED]

[REDACTED]

[REDACTED]

█ [REDACTED]

[REDACTED]

█ [REDACTED]

█ [REDACTED]

█ [REDACTED]

- | [REDACTED]
- | [REDACTED]
- | [REDACTED]
- | [REDACTED]
- | [REDACTED]
- | [REDACTED]
- | [REDACTED]
- | [REDACTED]
- | [REDACTED]
- | [REDACTED]
- | [REDACTED]

[REDACTED]
[REDACTED]
[REDACTED]

- | [REDACTED]
- | [REDACTED]
- | [REDACTED]
- | [REDACTED]
- | [REDACTED]
- | [REDACTED]
- | [REDACTED]
- | [REDACTED]

9.5.6.9 *Unscheduled Visits*

Unscheduled visits can be performed if safety concerns arise and at the discretion of the Investigator. Additional examinations may be performed as necessary to ensure the safety and well-being of the patients during the study.

9.6 DATA QUALITY ASSURANCE

9.6.1 Data Monitoring

Before any patient enters the study, a representative of the Sponsor will meet with the Investigator and the study center staff to review the procedures to be followed during the study. Electronic data capture (EDC) functionality training is provided via computer-based training to train investigators and authorized designees on recording the data in the eCRFs using the EDC system. After the first patient is enrolled, the Sponsor representative, a Regional Site Manager or designee, will periodically monitor the progress of the study by conducting on-site visits. This Regional Site Manager or designee will review query statuses remotely, possibly warranting more frequent communication and/or study center visits with the Investigator and the study center staff. The Investigator will make available to the Regional Site Manager or designee source documents (written notes and electronic medical records, if used), signed consent forms, and all other study-related documents. The Investigator and the study center staff will be responsible for data entry of patient data into the eCRFs via the EDC system, resolving data queries generated via the EDC system and providing missing or corrected data. The Investigator or designee will be responsible for approving all changes performed on the data, and endorsing the patient data within the EDC system. This approval method will include applying an electronic signature linked to a uniquely assigned username and password that together will represent a traditional handwritten signature used in the past.

9.6.2 Data Recording and Documentation

Data collection will involve the use of the EDC system, to which only authorized personnel will have access. Patient's data are to be entered into the EDC system by the Investigator or designee using their assigned EDC user account. After data entry into the EDC system by the Investigator or designee, a combination of manual and programmatic edit checks will be used to review the data for completeness, logic, and adherence to study protocol. As a result of these edit checks, data monitoring, and reviews, queries may be electronically issued to the study center and should be answered electronically via the EDC system.

Each query will carry identifying information (assigned username, date, and time) to assist the Sponsor and the Investigator on the origin of the data clarification request and the response provided by the Investigator. All data changes made to the patient's data via a data query will be approved by the Investigator prior to final database lock.

After all data have been reviewed and all issues have been resolved, the database will be locked.

All data collected in the context of this study will be stored and evaluated per regulatory requirements and applicable guidance for electronic records. Also, data will be stored and evaluated in such a way as to guarantee patient confidentiality in accordance with the legal stipulations applying to confidentiality of data. Study records (eg, copies of eCRFs, laboratory reports, and regulatory documents) will be retained at the study center, along with adequate source documentation, according to FDA and ICH requirements. All study records must be available for inspection by the Sponsor, its authorized representatives, the FDA, or other health authorities.

Data for the [REDACTED] C-SSRS, BPRS+, CADSS, and [REDACTED] will be captured using an electronic source tablet-based system. [REDACTED]

[REDACTED] Source documents will be used at the study centers and may include a patient's medical record, hospital charts, clinic charts, the Investigator's patient study files, as well as the results of diagnostic tests such as laboratory tests, ECGs, etc. A centralized clinical laboratory will be used for the analysis of all blood samples. Additional information on the collection and handling of samples is detailed in the Lab Procedure Manual.

9.7 STATISTICAL METHODS AND DETERMINATION OF SAMPLE SIZE

9.7.1 Analysis Populations

Three populations will be considered in the statistical analysis of the study, as specified in the following subsections.

9.7.1.1 Screened Population

The Screened Population will consist of all patients who signed the RAP-MD-06 ICF if they participated in Study RAP-MD-04, and all patients who underwent the Screening Visit, received a PID number, and signed the ICF if they didn't participate in Study RAP-MD-04.

9.7.1.2 Safety Population

The Safety Population will consist of all patients in the Screened Population who took at least 1 dose of rapastinel during the OLTP of the study.

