2.0 SYNOPSIS AND SCHEDULE OF EVALUATIONS

CLINICAL STUDY SYNOPSIS: Study RAP-MD-06	
Title of Study	An Open-label, Long-term Safety Study of Rapastinel as Adjunctive Therapy in Patients with Major Depressive Disorder
Study Centers (Country)	Approximately 105 to 110 study centers (United States)
Development Phase	3
Objective	To evaluate the long-term safety and tolerability of rapastinel as an adjunctive to antidepressant therapy (ADT) in patients with major depressive disorder (MDD)
Methodology	
Multicenter, open-label, long-term study in adult patients with a primary diagnosis of MDD.
 
For patients enrolling from RAP-MD-04, the final visit from that study (ie, Visit 122) will serve as Visit 1 in RAP-MD-06 and, after obtaining informed consent, open-label rapastinel will be administered at Visit 1 to ensure continuity of treatment.
 
The enrollment of patients who did not participate in RAP-MD-04 (identified as de novo enrollment patients) may be allowed at select study centers at the discretion of the Sponsor in the event that overall program enrollment indicates such de novo enrollment is necessary. Should de novo patients be enrolled with Sponsor approval, such patients will include adult patients with MDD who have no more than a partial response (defined as < 50% improvement) to ongoing ADT treatment in the current episode. Upon written informed consent, de novo enrollment patients will enter a screening period of up to 14 days.
 
Following the screening period, all patients will enter the 52-week Open-label Treatment Period (OLTP). The OLTP consists of weekly or biweekly (once every 2 weeks, based on Investigator discretion) visits for up to 52 weeks.
 
Upon completion of the OLTP, patients will enter a 2-week safety follow-up period.

Number of Patients	Approximately 500 patients are expected to enter the OLTP. The study will be terminated when 100 patients have completed the 52-week OLTP.

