Diagnosis and Main Criteria for Inclusion	
The following are requirements for entry into the study (patients entering from RAP-MD-04 are considered to have met inclusion criteria for diagnosis, severity, and prior ADT response, and are not required to meet these criteria upon entry into RAP-MD-06):
 
 • Male or female outpatients, ages 18 to 65 years who meet Diagnostic and Statistical Manual of Mental Disorders, Fifth Edition (DSM-5) criteria for MDD based on Structured Clinical Interview for Diagnostic Statistic Manual of Mental Health Disorders, Fifth Edition (SCID), with a current major depressive episode of at least 8 weeks and not exceeding 18 months in duration at Visit 1 • Have no more than partial response (< 50% improvement) to ongoing treatment with a protocol-allowed ADT ([REDACTED])

Test Product, Dosage, and Mode of Administration	Rapastinel 450 mg given intravenously (IV) either weekly or biweekly, per Investigator discretion, as adjunctive to ongoing ADT during the OLTP.
Duration of Treatment	For patients enrolling into RAP-MD-06 from RAP-MD-04 there will be a 1-week screening period, up to 52 weeks of open-label rapastinel as adjunctive treatment to ongoing ADT, and a 2-week safety follow-up period. Should de novo patients be enrolled at a later date, there will be a screening period of up to 2 weeks, up to 52 weeks of open-label rapastinel as adjunctive treatment to ongoing ADT, and a 2-week safety follow-up period.
Reference Therapy, Dosage, and Mode of Administration	None
Criteria for Evaluation	
[REDACTED]	[REDACTED]
[REDACTED]	[REDACTED]
Safety Measures	
 Adverse event (AE) recording, clinical laboratory measures, vital sign parameters, electrocardiograms (ECGs), and physical examinations Measure of psychotomimetic effects: Brief Psychiatric Rating Scale Positive Symptoms subscale (BPRS+) Measure of dissociative effects: Clinician Administered Dissociative States Scale (CADSS)
Pharmacokinetic Analysis	None
Pharmacogenetic Analysis	None
Statistical Methods	
Descriptive statistics will be presented for all efficacy and safety parameters. No inferential statistical analyses will be performed.
 
All safety parameters will be summarized for the Safety Population, defined as all patients who receive at least 1 dose of investigational product (IP) in this study.

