9.1.1 Screening

The screening period will occur up to 2 weeks prior to Visit 2:

- For patients enrolling from Study RAP-MD-04, the final visit from that study (Visit 122 [Week 104, ET]) will serve as Visit 1 in RAP-MD-06. These rollover patients will receive the first dose of open-label investigational product (IP) (ie, rapastinel 450 mg IV) at Visit 1 to ensure continuity of treatment.
- Upon providing written informed consent, *de novo* patients will enter a screening period of up to 14 days. *De novo* patients will not receive any IP during the screening period but must continue their background ADT at the same dose and wash out of prohibited medications ([Appendix III](#)). *De novo* patients meeting the eligibility criteria at the end of Visit 2 (Baseline) will be assigned a treatment by IWRS and enter the OLTP.

All patients will maintain usage of their ADT throughout participation in the study (see [Section 9.4.10.1](#)).

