9.1.2 Open-label Treatment Period

Approximately 500 patients are planned for enrollment in the OLTP; all patients will receive open-label rapastinel at 450 mg IV (adjunctive to ADT), either weekly or once every 2 weeks, based upon the Investigator's discretion. Patients will skip odd-numbered visits if being treated on a biweekly basis). The once-every-2-weeks schedule can only be initiated on even-numbered visits in order to maintain the appropriate visit schedule. Patients who are on a once-every-2-weeks schedule can be transitioned back to weekly visits at any visit.

Upon completion of the OLTP at Visit 54 (Week 52, ET), patients will enter a 2-week safety follow-up period and will return to the clinic at Visit 55 (Week 54). The maximum duration of the study will be 56 weeks.

The study will be terminated when 100 patients have completed the 52-week OLTP.

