9.4.7.1 Screening Period

For patients enrolling from RAP-MD-04, the final visit from that study (Visit 122 [Week 104, ET]) will serve as Visit 1 in this study, after written consent is obtained. Rollover patients will receive open-label IP at Visit 1 to ensure continuity of treatment.

For *de novo* patients, at Visit 1, after written consent is obtained, patients will enter a screening period of up to 14 days. No IP is administered to *de novo* patients during the screening period; however, patients must continue their background ADT at a stable dose. During this time *de novo* patients will wash out of prohibited medications, per [Appendix III](#).

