9.7.6 Safety Analyses

The safety analysis will be performed using the Safety Population, defined as all patients who receive at least 1 dose of IP during the OLTP.

The safety parameters will include AEs; clinical laboratory, vital signs, and ECG parameters; and the BPRS+, CADSS, [REDACTED].

For each safety parameter, the last assessment made before the first dose of open-label IP will be used as the baseline for *de novo* patients, and the baseline of the first lead-in study will be used as the baseline for rollover patients for all analyses of that safety parameter. Continuous variables will be summarized by number of patients and mean, SD, median, minimum, and maximum values. Categorical variables will be summarized by number and percentage of patients.

9.7.6.1 *Adverse Events*

AEs will be coded by system organ class (SOC) and preferred term using the *Medical Dictionary for Regulatory Activities*.

For rollover patients, an AE (classified by preferred term) that occurs during the OLTP will be considered a treatment-emergent adverse event (TEAE) if it was not present before the first dose of IP in the first lead-in study or was present before the first dose of IP in the first lead-in study and increased in severity during the OLTP. If more than 1 AE is reported before the first dose of IP in the first lead-in study and coded to the same preferred term, the AE with the greatest severity will be used as the benchmark for comparison with the AEs occurring during the OLTP that were also coded to that preferred term.

For *de novo* patients, an AE (classified by preferred term) that occurs during the OLTP will be considered a TEAE if it was not present before the first dose of open-label IP or was present before the date of the first dose of open-label IP and increased in severity after the first dose of open-label IP. If more than 1 AE is reported before the first dose of open-label IP and is coded to the same preferred term, the AE with the greatest severity will be used for comparison with the AEs occurring during the OLTP that were also coded to that preferred term.

An AE that occurs more than 30 days after the date of the last dose of IP will not be considered a TEAE.

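### The Safety Population is defined in two ways, and read literally the body text leaves out rollover patients dosed at Visit 1 and stopped at Visit 2

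*Protocol*

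**What the plan says.** Three places in the protocol define the Safety Population.

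- Synopsis, Statistical Methods: "defined as all patients who receive at least 1 dose of investigational product (IP) in this study".
- Section 9.7.1.2: "all patients in the Screened Population who took at least 1 dose of rapastinel during the OLTP of the study".
- Section 9.7.6: "defined as all patients who receive at least 1 dose of IP during the OLTP".

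The first has no period restriction. The other two require a dose inside the OLTP.

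On the rollovers' first dose, section 9.4.7.1, headed Screening Period, states: "Rollover patients will receive open-label IP at Visit 1 to ensure continuity of treatment". Section 9.1.1 also describes this dose under Screening and says of that period: "The screening period will occur up to 2 weeks prior to Visit 2". The synopsis gives rollovers a screening period of their own: "For patients enrolling into RAP-MD-06 from RAP-MD-04 there will be a 1-week screening period, up to 52 weeks of open-label rapastinel".

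Inclusion criterion 8 in section 9.3.1 and the note opening section 9.3.2 recognise that Visit 1 results arrive after the Visit 1 dose. They allow a rollover to be discontinued at Visit 2 for a positive pregnancy test or for laboratory or ECG concerns.

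Section 9.7.6.1 limits treatment-emergent adverse events (TEAEs) to events in the OLTP, and a newly emergent adverse event (NEAE) must first be a TEAE. By contrast, exposure (9.7.4.1) and on-therapy serious adverse events (9.7.6.1) run from the first open-label dose.

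**The concern.** Safety is the study's only objective, and its summary tables are built on this population. The definitions differ for an identifiable group: rollovers who received one open-label dose and were then stopped because of a result from the day of that dose. Patients stopped for a safety result after treatment should not be in or out of the denominator according to which section the programmer reads.

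Under the OLTP wording such a patient also drops out of the disposition table by reason, which section 9.7.2 bases on the Safety Population. The screen-failure table in the same section covers de novo patients only, so neither table would give the reason for stopping.

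For rollovers who continue, the first week of open-label treatment would count as exposure, while non-serious events that start and end within that week would not count as TEAEs.

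**Working it through.** **1. The protocol's own duration figure.** Section 9.1.2 states: "The maximum duration of the study will be 56 weeks". Up to 2 weeks of screening + 52 weeks of OLTP + 2 weeks of follow-up = 56, so the figure reproduces. It reflects the de novo maximum. For a rollover the sum is 1 + 52 + 2 = 55 weeks, so the 56-week figure cannot show where the rollovers' OLTP starts.

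**2. Where the OLTP starts.** Section 9.4.7.2 equates Visit 53 with Week 51, and section 9.1.2 equates Visit 54 with Week 52. With weekly visits, week = visit − 2.

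- Visit 2 = Week 0. From there to Visit 54 is 52 weeks, the stated OLTP length.
- Starting at a rollover's Visit 1, one week earlier, would give 53 weeks and leave no room for the 1-week screening period in the synopsis.

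The design sections therefore place the Visit 1 dose one week before the OLTP.

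**3. Consequence for a rollover stopped at Visit 2.** Doses in the study: 1. Doses in the OLTP: 0. The patient is in the Safety Population by the synopsis and out by 9.7.1.2 and 9.7.6.

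**4. Consequence for adverse events in a rollover who continues.** Take a non-serious event that starts after the Visit 1 dose and resolves before Visit 2. It does not occur in the OLTP, so it is neither a TEAE nor an NEAE. An event still present at Visit 2 is not lost in this way.

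**5. Bounds on size.** The protocol gives no Visit 2 stop rate and no event rate.

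- *Incidence.* Let n rollovers be dosed and k of them excluded. Let x have an event, j of those among the k. The difference |x/n − (x − j)/(n − k)| is at most k/n. Per excluded patient this is 1/500 = 0.2 percentage points at n = 500 and 1/250 = 0.4 points at n = 250 (an assumed lower rollover count).
- *Stop rate, purely as an assumption.* If all 500 were rollovers, 0.5% to 5% stopping at Visit 2 would be 2.5 to 25 dosed patients.
- *Common-TEAE cut-off (2% or more).* 10/500 = 2.0% is listed. 9/500 = 1.8% (event not counted) or 9/499 = 1.8% (patient excluded) is not. This is a boundary case, not a typical one.
- *Dose share for a completer.* Weekly: 52 doses at Visits 2 to 53 plus Visit 1 = 53, and 1/53 = 1.9%. Biweekly: 26 doses at even visits 2 to 52 plus Visit 1 = 27, and 1/27 = 3.7%.
- *Time.* At most 500 × 7/365.25 = 9.6 patient-years, if all 500 were rollovers.

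**The case against.** The best defence is that the analysis text already treats the first open-label dose as the start of the OLTP.

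- Section 9.7.4.1 measures OLTP exposure from that dose and words its concomitant-medication rule as if the dose lay inside the OLTP.
- Section 9.4.7.2 mentions the Visit 1 dose under the OLTP heading.
- Section 9.7.2 tabulates screen failures for de novo patients only, which fits a plan in which every dosed rollover is in the Safety Population.
- The 30-day limit on TEAEs would add little for completers if the OLTP were a strict Visit 2 to Visit 54 window.

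The Schedule of Evaluations, the design figure and the visit-by-visit descriptions are also not visible and might label Visit 1 differently for rollovers.

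Most of this stands as evidence of intent, and it makes the loss conditional on a literal reading. It does not remove the contradiction. Section 9.4.7.2 still ties dosing in the OLTP to eligibility at Visit 2, the visit arithmetic agrees with that, and no visible sentence says that a rollover's OLTP starts at Visit 1. A conflict between stated population definitions is also not a detail left to the analysis plan.

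A reader might infer that the whole first week is ignored for rollovers but counted for de novo patients. The documents do not support that: only non-serious events that both start and resolve before Visit 2 are affected. Nor do they show an error in the denominators for potentially clinically significant values or in the compliance rules.

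**Conclusion.** The protocol contradicts itself on the main population of a safety-only study. The conflict affects treated rollovers stopped at Visit 2 and, through the TEAE definition, brief non-serious events in the first week after the Visit 1 dose. Both losses arise only if the OLTP is taken to start at Visit 2, as the design sections have it.

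The number affected cannot be derived and is probably small. The bound is k/n on any incidence, or 0.2 percentage points per excluded patient among 500.

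A reader might go further and conclude that serious harm would be hidden or that the exclusion is deliberate. Neither follows. The windows for on-therapy serious events and potential Hy's Law cases open at the first dose. The listings of serious events and of discontinuations for adverse events also cover events outside the OLTP. The analysis wording points to an intention to count the Visit 1 dose. The study remains valid, but the text should be corrected before the tables are programmed.

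**What to change.** 1. Use the synopsis definition throughout: all patients with at least 1 dose of open-label rapastinel in RAP-MD-06. Delete the OLTP restriction from 9.7.1.2 and 9.7.6.
2. In 9.7.6.1, let the window for TEAEs and NEAEs open at the first open-label dose in this study (Visit 1 for rollovers, Visit 2 for de novo patients), so that onset or worsening on or after that dose counts. Keep the existing pre-treatment benchmarks and the 30-day limit after the last dose.
3. In 9.7.2, report rollovers stopped at Visit 2 as treated discontinuations, with their reason.

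The 52-week OLTP visit schedule, the denominators for potentially clinically significant values and the compliance rules need no change.

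The cost is a few edited sentences and matching programming. Injection dates (9.4.12) and adverse events from consent (9.5.2.1) are already collected, so no patients, visits or data are added.
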